5.4.3 Other allowed dose interruptions for pembrolizumab

Pembrolizumab may be interrupted for situations other than treatment-related AEs such as medical / surgical events or logistical reasons not related to study therapy. Participants should be placed back on study therapy within 6 weeks of the scheduled interruption, unless otherwise discussed with the Sponsor. The reason for interruption should be documented in the patient's study record.

5.4.3.1 Second Course *

All participants who stop study treatment with SD or better may be eligible for up to an additional 17 cycles (approximately 1 year) of pembrolizumab treatment if they progress after stopping study treatment from the initial treatment phase. This retreatment is termed the Second Course Phase of this study and is only available if the study remains open and the participant meets the following conditions:

Either

- Stopped initial treatment with study treatment after attaining an investigator-determined confirmed CR based on RECIST 1.1, and
 - Was treated with at least 8 cycles of study treatment before discontinuing treatment, and
 - Received at least 2 treatments with pembrolizumab beyond the date when the initial CR was declared

OR

- Had SD, PR, or CR and stopped study treatment after completion of 35 administrations (approximately 2 years) of study treatment for reasons other than disease progression or intolerance

AND

- Experienced an investigator-determined radiographic disease progression by RECIST 1.1 after stopping initial treatment, and
 - No new anticancer treatment was administered after the last dose of study treatment, and
 - The participant meets all of the safety parameters listed in the inclusion criteria and none of the safety parameters listed in the exclusion criteria, and
 - The study is ongoing

A Phase II, Single-arm Study of Combination Pembrolizumab and Olaparib in the Treatment of

Patients with Advanced Cholangiocarcinoma

Version 2.1: 17Mar2023

An objective response or disease progression that occurs during the Second Course Phase for a participant will not be counted as an event for the primary analysis of either endpoint in this study.

**Note: patients must have measurable disease at the start of protocol treatment to be eligible for this provision.*

5.4.3.2: Re-challenge with Pembrolizumab treatment

If patient's pembrolizumab treatment is discontinued for immune mediated AEs, when patient's immune mediated AEs have resolved or improved to grade 1, if patient will likely benefit from the treatment and it is safe to restart Pembrolizumab treatment per treating physician's assessment, patient is allowed to resume pembrolizumab treatment and follow the procedures per protocol.

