5.4.1 Timing of Dose Administration

Trial treatment should be administered on Day 1 of each cycle after all procedures/assessments have been completed as detailed on the Trial Flow Chart (Section 6.0). Trial treatment may be administered up to 3 days before or after the scheduled Day 1 of each cycle due to administrative reasons.

All trial treatments will be administered on an outpatient basis. There are no pre-medications for olaparib or pembrolizumab.

A Phase II, Single-arm Study of Combination Pembrolizumab and Olaparib in the Treatment of Patients with Advanced Cholangiocarcinoma
Version 2.1: 17Mar2023

Patient will be treated with olaparib at 300 mg by mouth twice per day continuously in combination with pembrolizumab at 200 mg administered intravenously every three weeks. Sites should make every effort to target infusion timing to be as close to 30 minutes as possible. However, given the variability of infusion pumps from site to site, a window of -5 minutes and +10 minutes is permitted (i.e., infusion time is 30 minutes: -5 min/+10 min).

The Pharmacy Manual contains specific instructions for the preparation of the pembrolizumab infusion fluid and administration of infusion solution.

5.4.2 Dose Modification and toxicity management for immune-related AEs associated with pembrolizumab

AEs associated with pembrolizumab exposure may represent an immunologic etiology. These immune-related AEs (irAEs) may occur shortly after the first dose or several months after the last dose of pembrolizumab treatment and may affect more than one body system simultaneously. Therefore, early recognition and initiation of treatment is critical to reduce complications. Based on existing clinical study data, most irAEs were reversible and could be managed with interruptions of pembrolizumab, administration of corticosteroids and/or other supportive care. For suspected irAEs, ensure adequate evaluation to confirm etiology or exclude other causes. Additional procedures or tests such as bronchoscopy, endoscopy, skin biopsy may be included as part of the evaluation. Based on the severity of irAEs, withhold or permanently discontinue pembrolizumab and administer corticosteroids. Dose modification and toxicity management guidelines for irAEs associated with pembrolizumab are provided in Table 3. NOTE: During management of any irAEs, Olarparib treatment may continue subject to physician discretion.

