Table 3 Dose modification and toxicity management guidelines for immune-related AEs associated with pembrolizumab

General instructions:				
Immune-related AEs	Toxicity grade or conditions (CTCAE v4.0)	Action taken to pembrolizumab	irAE management with corticosteroid and/or other therapies	Monitor and follow-up
Pneumonitis	Grade 2	Withhold	
 Administer corticosteroids (initial dose of 1-2 mg/kg prednisone or equivalent) followed by taper 	
 Monitor participants for signs and symptoms of pneumonitis Evaluate participants with suspected pneumonitis with radiographic imaging and initiate corticosteroid treatment Add prophylactic antibiotics for opportunistic infections
	Grade 3 or 4, or recurrent Grade 2	Permanently discontinue		
Diarrhea / Colitis	Grade 2 or 3	Withhold	
 Administer corticosteroids (initial dose of 1-2 mg/kg prednisone or equivalent) followed by taper 	
 Monitor participants for signs and symptoms of enterocolitis (i.e., diarrhea, abdominal pain, blood or mucus in stool with or without fever) and of bowel perforation (i.e., peritoneal signs and ileus).

A Phase II, Single-arm Study of Combination Pembrolizumab and Olaparib in the Treatment of Patients with Advanced Cholangiocarcinoma
 Version 2.1: 17Mar2023

	Grade 4	Permanently discontinue		
 Participants with \geq Grade 2 diarrhea suspecting colitis should consider GI consultation and performing endoscopy to rule out colitis. Participants with diarrhea/colitis should be advised to drink liberal quantities of clear fluids. If sufficient oral fluid intake is not feasible, fluid and electrolytes should be substituted via IV infusion.
AST / ALT elevation or Increased bilirubin	Grade 2	Withhold	
 Administer corticosteroids (initial dose of 0.5- 1 mg/kg prednisone or equivalent) followed by taper 	
 Monitor with liver function tests (consider weekly or more frequently until liver enzyme value returned to baseline or is stable
	Grade 3 or 4	Permanently discontinue	
 Administer corticosteroids (initial dose of 1-2 mg/kg prednisone or equivalent) followed by taper 	

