5.6 Participant Withdrawal/Discontinuation Criteria

Participants may discontinue study treatment at any time for any reason or be dropped from the study treatment at the discretion of the investigator should any untoward effect occur. In addition, a participant may be discontinued from study treatment by the investigator or the Sponsor if study treatment is inappropriate, the trial plan is violated, or for administrative and/or other safety reasons. Specific details regarding procedures to be performed at study treatment discontinuation are provided in Section 7.1.4 – Other Procedures.

A participant must be discontinued from study treatment but continue to be monitored in the study for any of the following reasons:

- The participant or participant's legally acceptable representative requests to discontinue study treatment
- Confirmed radiographic disease progression outlined in Section 7.1.2.6
- Any progression or recurrence of any malignancy, or any occurrence of another malignancy that requires active treatment
- Unacceptable adverse experiences as described in Section 5.2.2.
- The participant has a medical condition or personal circumstance that, in the opinion of the investigator and/or sponsor, placed the participant at unnecessary risk from continued administration of study treatment.
- The participant has a confirmed positive serum pregnancy test
- Noncompliance with study treatment or procedure requirements

A Phase II, Single-arm Study of Combination Pembrolizumab and Olaparib in the Treatment of

Patients with Advanced Cholangiocarcinoma

Version 2.1: 17Mar2023

- Recurrent Grade 2 pneumonitis
- Discontinuation of treatment may be considered for participants who have attained a confirmed complete response (CR) and have been treated for at least 8 cycles (at least 24 weeks), receiving 2 doses of pembrolizumab and at least 80% of the planned doses of olaparib beyond the date when the initial CR was declared. These participants may be eligible for second course treatment described in Section 5.2.3.
- The participant is lost to follow-up
- Completion of 35 treatments (approximately 2 years) with pembrolizumab

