Note: The number of treatments is calculated starting with the first dose. Participants who stop the combination or pembrolizumab after receiving 35 doses may be eligible for retreatment if they progress after stopping study treatment provided they meet the requirements detailed in Section 5.2.3. Participants may be retreated in the Second Course Phase (Retreatment) for up to an additional 17 cycles (approximately 1 year).

- Administrative reasons

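### Section 5.4.3.2 permits pembrolizumab re-challenge after any immune-mediated discontinuation, without stating its relation to Table 3's permanent stops or excluding any event, even Grade 3–4 myocarditis

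*Combined protocol and SAP*

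**What the plan says.** Section 5.4.2 sets the general rule for immune-related AEs: depending on severity, "withhold or permanently discontinue pembrolizumab and administer corticosteroids". Table 3 applies it event by event. Some rows say withhold, some say continue, and six groups carry a plain instruction to discontinue permanently. Footnote 1, which leaves the choice to the investigator or treating physician, is attached only to Grade 3–4 hypophysitis and Grade 3–4 hyperthyroidism. A note under the table lets pembrolizumab resume after Grade 3–4 endocrinopathies for which it was withheld, once the event is at Grade 2 or lower and controlled.

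Section 5.4.3.2 provides for re-challenge when pembrolizumab has been discontinued for immune-mediated AEs. If the events have resolved or improved to Grade 1, and the treating physician judges that benefit is likely and restart is safe, the "patient is allowed to resume pembrolizumab treatment and follow the procedures per protocol".

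Section 5.6 contains a list introduced by "A participant must be discontinued from study treatment but continue to be monitored in the study for any of the following reasons". One entry is "Recurrent Grade 2 pneumonitis".

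Table 7 (Section 7.2.4), in its rechallenge row, requires advance sponsor approval in two situations: the AE was serious and may have been caused by the product, or re-exposure poses additional significant risk. It says that this approval follows the protocol's dose-modification guidelines.

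**The concern.** Take a patient who has recovered from Grade 3 myocarditis. Table 3 says that pembrolizumab is stopped for good. Section 5.4.3.2, read on its own, allows a restart on the treating physician's assessment. A site cannot tell from these two places whether a restart would follow the protocol or deviate from it.

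What is at stake is patient safety in a small number of severe cases. Section 9.1.1.1.7 names myocarditis as a new important risk with fatal cases, and lists other immune-mediated risks, some with fatal outcome. Section 5.4.3.2 is where the restart decision is made. It neither excludes the most dangerous events nor refers the physician to the sponsor-approval step in Table 7.

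**Working it through.** No design figure in the plan bears on this point, so the check is a row count of Table 3 and a side-by-side reading.

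**Step 1: Table 3 entries that direct permanent discontinuation, with no discretion footnote.**

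| Group | Grade that triggers the permanent stop |
|---|---|
| Pneumonitis | 3–4, or recurrent 2 |
| Diarrhea/colitis | 4 |
| AST/ALT or bilirubin | 3–4 |
| Nephritis/renal dysfunction | 3–4 |
| Myocarditis | 3–4 |
| All other immune-related AEs | 4, or recurrent 3 |

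The count is six. Hypophysitis and hyperthyroidism at Grade 3–4 are discretionary, type 1 diabetes/hyperglycemia is withhold only, and hypothyroidism is continue. Within the last group, Guillain-Barre syndrome and encephalitis are named as Grade 3 events that require discontinuation, though that row does not use the word permanent.

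**Step 2: scope of Section 5.4.3.2.** The trigger is discontinuation for immune-mediated AEs. No AE type or grade is excluded, and withheld patients are not distinguished from permanently discontinued ones. There are three conditions: recovery to Grade 1 or better, likely benefit, and a safety judgement by the treating physician.

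**Step 3: links between the two.** Section 5.4.3.2 names neither Table 3, Section 5.6, Table 7 nor the sponsor. It has only the general phrase about following protocol procedures, and Table 3 is itself one of those procedures. The resumption note under Table 3 concerns withheld endocrinopathies, so it does not settle the matter. Table 3 also opens with a heading, "General instructions", whose content is missing from the text available for this review. It could contain a restart rule and should be checked.

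**Step 4: the approval route.** Table 7 defers to the dose-modification guidelines. The visible guidelines (Section 5.4.2, Table 3 and Section 5.4.3.2) contain no approval step. A reader who starts from Table 7 is sent to text that does not mention approval; a reader who starts from Section 5.4.3.2 is not sent to Table 7.

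**Step 5: scale, as illustration only.** The documents give no rate of immune-related discontinuation or re-challenge for this combination. Section 4.2.1.2.1 gives 11.9% discontinuation for AEs in the pembrolizumab reference data. If that rate applied here, 36 × 0.119 = 4.28 patients would discontinue for any AE. Let s be the share of these in one of the six groups and r the share of those considered for re-challenge. Both are assumed to lie between 10% and 50%.

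- s = r = 0.10: 36 × 0.119 × 0.10 × 0.10 = 0.04 patients
- s = r = 0.25: 36 × 0.119 × 0.25 × 0.25 = 0.27 patients
- s = r = 0.50: 36 × 0.119 × 0.50 × 0.50 = 1.07 patients

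This shows only that the number is small. With two assumed shares and a rate from other settings, it carries no weight in the conclusion.

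**The case against.** The best answer is that Section 5.4.3.2 is a deliberate exception. It is headed as re-challenge, and its trigger is discontinuation, which Table 3 distinguishes from withholding. A section that merely repeated the resume-after-withhold rule would not need that wording. Table 3 also describes itself as guidelines. This reading is plausible, so a flat contradiction is not shown. What stands is that the exception is not stated and has no limit.

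A reader might infer that Section 5.6 independently forbids restart, since recurrent Grade 2 pneumonitis is on its mandatory list. The documents do not support that. The same section includes stops after which retreatment is allowed. For patients who stop after a confirmed CR it says "These participants may be eligible for second course treatment described in Section 5.2.3" (the Second Course text is now Section 5.4.3.1), and it adds that "Participants who stop the combination or pembrolizumab after receiving 35 doses may be eligible for retreatment". Being listed there does not by itself bar resumption. That Section 5.6 names no return route after an immune-mediated AE is silence, not a prohibition.

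A reader might also infer that re-challenge after a severe event needs only the treating physician. That too goes too far. Table 7's approval is mandatory when its conditions are met, and Grade 3–4 myocarditis would ordinarily meet them; the rule does not lapse because Section 5.4.3.2 fails to cite it. Section 5.6 also requires stopping treatment where a condition "placed the participant at unnecessary risk from continued administration of study treatment". Section 10.1.4 adds real-time monitoring by the principal investigator and semi-annual committee review. These safeguards reduce the consequence, but they do not tell the physician which Table 3 stops are final.

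Finally, no part of the protocol says which events may never be re-challenged, so any barred list is a clinical choice. That is correct, and the list proposed here is a minimum for the sponsor to confirm.

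**Conclusion.** The point holds as a gap in the wording with a patient-safety consequence. Table 3 directs permanent discontinuation in six groups. Section 5.4.3.2 permits restart after any immune-mediated discontinuation that has recovered to Grade 1 or better, without saying that it overrides Table 3 and without excluding any event. Followed as written, it permits restart after Grade 3–4 myocarditis. Sponsor approval already exists in Table 7 and would cover most such cases, so the defect there is a missing pointer in both directions, not missing oversight.

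Few patients are likely to be affected, and there is no effect on sample size or analysis. The change is worth making because the events are severe and the amendment is cheap. The conclusion assumes that the unseen general instructions in Table 3 do not already settle the order of precedence; if they do, only the cross-references remain to be added.

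**What to change.** Amend Section 5.4.3.2 as follows.

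1. State that it is an exception to Table 3's permanent-discontinuation entries, except for life-threatening non-endocrine events, where permanent discontinuation stands. At minimum these are Grade 3–4 myocarditis, Grade 3–4 or recurrent Grade 2 pneumonitis, Guillain-Barre syndrome and encephalitis.
2. Leave Grade 4 endocrinopathies under the existing resumption note below Table 3. A blanket bar on Grade 4 events would clash with that note.
3. For every other event that Table 3 says to stop permanently, allow re-challenge only with the advance sponsor approval described in Table 7, and cite Table 7 in Section 5.4.3.2. This applies the approval step to all these events, including any that would not meet Table 7's own conditions.

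The cost is a wording amendment and somewhat less discretion for the treating physician to restart. Visits, sample size and analysis do not change.

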5.5 Concomitant Medications/Vaccinations (allowed & prohibited)

Medications or vaccinations specifically prohibited in the exclusion criteria are not allowed during the ongoing trial. If there is a clinical indication for one of these or other medications or vaccinations specifically prohibited during the trial, discontinuation from trial therapy or vaccination may be required. The final decision on any supportive therapy or vaccination rests with the investigator and/or the participant's primary physician.

5.5.1 Acceptable Concomitant Medications

All treatments that the investigator considers necessary for a participant's welfare may be administered at the discretion of the investigator in keeping with the community standards of medical care. All concomitant medication will be recorded on the case report form (CRF) including all prescription, over-the-counter (OTC), herbal supplements, and IV medications and fluids. If changes occur during the trial period, documentation of drug dosage, frequency, route, and date may also be included on the CRF.

All concomitant medications received within 28 days before the first dose of trial treatment and 30 days after the last dose of trial treatment should be recorded. Concomitant medications administered after 30 days after the last dose of trial treatment should be recorded for SAEs and ECIs as defined in Section 7.2.

Considering olaparib treatment, avoid concomitant use of strong and moderate CYP3A inhibitors and consider alternative agents with less CYP3A inhibition. If the inhibitor cannot be avoided, reduce the olaparib dose to 150 mg twice daily for a strong CYP3A inhibitor or 200 mg twice daily for a moderate CYP3A inhibitor. (see FDA package insert of Olaparib).

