Following oral administration of olaparib via the capsule formulation, absorption is rapid with peak plasma concentrations typically achieved between 1 to 3 hours after dosing. On multiple dosing there is no marked accumulation (accumulation ratio of 1.4- 1.5 for twice daily dosing), with steady state exposure achieved within 3 to 4 days.

Co-administration with a high fat meal slowed the rate (Tmax delayed by 2 hours) of absorption, but did not significantly alter the extent of olaparib absorption (mean AUC increased by approximately 20%). Therefore there is no restriction with diet while olaparib is administered.

Drug interactions:

In vitro, olaparib was an inhibitor of CYP3A4 and an inducer of CYP2B6, but these activities occurred at higher concentrations than are clinically achieved. Olaparib produced little/no

A Phase II, Single-arm Study of Combination Pembrolizumab and Olaparib in the Treatment of Patients with Advanced Cholangiocarcinoma

Version 2.1: 17Mar2023

inhibitions of other CYP isozymes. In vitro studies have shown that olaparib is a substrate of CYP3A4.

Based on the data from a drug-interaction trial (N=57), the AUC and Cmax of Olaparib increased by 2.7- and 1.4-fold, respectively, when Olaparib was administered in combination with itraconazole, a strong CYP3A inhibitor. Simulations using physiologically-based pharmacokinetic (PBPK) models suggests that a moderate CYP3A inhibitor (fluconazole) may increase the AUC and Cmax of Olaparib by 2- and 1.1-fold, respectively.

Based on the data from a drug-interaction trial (N=22), the AUC and Cmax of Olaparib decreased by 87% and 71%, respectively, when Olaparib was administered in combination with rifampicin, a strong CYP3A inducer. Simulations using PBPK models suggested that a moderate CYP3A inducer (efavirenz) might decrease the AUC and Cmax of Olaparib by 50-60% and 20-30%, respectively.

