4.3.2.2 Effect of other drugs on olaparib

CYP3A4/5 are the isozymes predominantly responsible for the metabolic clearance of olaparib. Clinical studies conducted with a tablet formulation to evaluate the impact of known CYP3A inhibitors and inducers have shown that co-administration of a potent CYP3A inhibitor, itraconazole, increased olaparib Cmax by 142% (90% CI: 1.33-1.52) and increased mean AUC by 270% (90% CI: 2.44-2.97) and that co-administration of a potent CYP inducer, rifampicin, decreased Cmax by 71% (treatment ratio: 0.29; 90% CI: 0.24-0.33) and mean AUC by 87% (treatment ratio: 0.13; 90% CI: 0.11-0.16). Moderate inhibitors and inducers of CYP3A are also predicted to significantly alter the exposure of olaparib. It is therefore recommended that known strong CYP3A inhibitors (e.g., itraconazole, telithromycin, clarithromycin, boosted protease inhibitors, indinavir, saquinavir, nelfinavir, boceprevir, telaprevir) or moderate CYP3A inhibitors (ciprofloxacin, erythromycin, diltiazem, fluconazole, verapamil) should not be taken with olaparib.

If there is no suitable alternative concomitant medication then the dose of olaparib or study treatment should be reduced for the period of concomitant administration. With strong CYP3A inhibitors, the dose of olaparib tablet formulation should be reduced from 300 mg bid to 100 mg bid for the duration of concomitant therapy with the strong inhibitor and for 5 half-lives of the concomitant medication after stopping its treatment. With moderate CYP3A inhibitors, the dose of the tablet formulation should be reduced from 300 mg bid to 150 mg bid for the duration of concomitant therapy with the moderate inhibitor and for 3 half-lives of the concomitant medication

A Phase II, Single-arm Study of Combination Pembrolizumab and Olaparib in the Treatment of Patients with Advanced Cholangiocarcinoma

Version 2.1: 17Mar2023

after stopping its treatment. After the washout of the inhibitor is complete, the olaparib dose can be re-escalated.

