⁴ FOR WOMEN OF CHILDBEARING POTENTIAL (WOCBP): URINE OR SERUM BHCG, WITHIN 28 DAYS OF REGISTRATION AND ONLY IF CLINICALLY APPROPRIATE. IF A URINE TEST IS DONE AND IT IS POSITIVE OR CANNOT BE CONFIRMED AS NEGATIVE, A SERUM PREGNANCY TEST WILL BE REQUIRED.

⁵ RADIOLOGY IMAGING FOR DISEASE ASSESSMENT WILL BE PERFORMED AT THE FOLLOWING TIME POINTS: SCREENING, EVERY SIX WEEKS WITHIN THE 24 WEEKS FROM THE START OF TREATMENT, THEN EVERY NINE WEEKS UP TO 12 MONTHS FROM THE START OF TREATMENT, THEN EVERY TWELVE WEEKS UP TO 24 MONTHS. FOR PATIENTS WHO DO NOT HAVE RADIOGRAPHIC PROGRESSION: RADIOLOGY IMAGING OR REPORT SHOULD BE OBTAINED EVERY 12 WEEKS THEREAFTER UNTIL DISEASE (RADIOGRAPHIC) PROGRESSION IF POSSIBLE. MRI OF THE BRAIN SHOULD ONLY BE DONE IF THE PATIENT IS SUSPECTED TO HAVE A BRAIN LESION.

A Phase II, Single-arm Study of Combination Pembrolizumab and Olaparib in the Treatment of Patients with Advanced Cholangiocarcinoma
Version 2.1: 17Ma2023

⁶ OLAPARIB WILL START ON C1D1 AND CONTINUE TWICE DAILY. PEMBROLIZUMAB WILL START C1D1 AND CONTINUE EVERY 3 WEEKS. PLEASE SEE SECTION 5 FOR DETAILS REGARDING OLAPARIB AND PEMBROLIZUMAB ADMINISTRATION.

⁷ ALL SUBJECTS WILL HAVE A BIOPSY PERFORMED OF A SAFELY ACCESSIBLE TUMOR BEFORE STARTING TREATMENT (WITHIN 42 DAYS OF STARTING TREATMENT ON THIS PROTOCOL) AND THE 3RD WEEK PRIOR TO 2ND DOSE OF PEMBROLIZUMAB, AND AT THE TIME OF CANCER PROGRESSION. SUBJECTS FOR WHOM NEWLY OBTAINED SAMPLES CANNOT BE PROVIDED (E.G. INACCESSIBLE OR SUBJECT SAFETY CONCERN) MAY SUBMIT AN ARCHIVED SPECIMEN ONLY UPON AGREEMENT FROM THE SPONSOR-INVESTIGATOR. SUBSEQUENT BIOPSIES CAN BE WAIVED BY SPONSOR-INVESTIGATOR FOR SAFETY CONCERNS OF THE BIOPSY PROCEDURE.

⁸ SERIAL BLOOD SAMPLES WILL BE COLLECTED TO SUPPORT BIOMARKER RESEARCH AT THE FOLLOWING TIME POINTS: PRIOR TO TREATMENT (1) C1D1, (2) C2D1, (3)C3D1 AND (5) FOLLOW UP VISIT 1. SEE CLM FOR ADDITIONAL DETAILS.

⁹ THIS TESTING IS TO BE DONE PRIOR TO EACH PEMBROLIZUMAB TREATMENT.

¹⁰ CARBOHYDRATE ANTIGEN (CA) 19-9 WILL BE DRAWN EVERY OTHER CYCLE STARTING AT CYCLE 1 (E.G. CYCLE 1, CYCLE 3, CYCLE 5, ETC).

¹¹ FOLLOW UP FOR PATIENTS THAT HAVE NOT EXPERIENCED PROGRESSION WILL OCCUR EVERY 12 WEEKS \pm 7 DAYS; THIS MAY BE DONE BY PHONE CALL OR OTHER AVENUES, AS APPROPRIATE. EVERY EFFORT SHOULD BE MADE TO OBTAIN INFORMATION ON RADIOLOGY SCANS OR OTHER TYPES OF DISEASE ASSESSMENT DOCUMENTATION.

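### Sections 5.5.1 and 4.3.2.2 give different olaparib doses for an unavoidable CYP3A inhibitor; the 5.5.1 doses probably leave AUC above the full-dose level

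*Combined protocol and SAP*

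**What the plan says.** Section 5.5.1 first asks sites to avoid strong and moderate CYP3A inhibitors. If that is impossible, they are to "reduce the olaparib dose to 150 mg twice daily for a strong CYP3A inhibitor or 200 mg twice daily for a moderate CYP3A inhibitor". It refers to the FDA package insert, names no formulation, and says nothing about how long the reduction lasts.

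Section 4.3.2.2 also starts from avoidance. Where there is no suitable alternative, it says for strong inhibitors that "the dose of olaparib tablet formulation should be reduced from 300 mg bid to 100 mg bid", and for moderate inhibitors that "the dose of the tablet formulation should be reduced from 300 mg bid to 150 mg bid". The reduction continues for 5 (strong) or 3 (moderate) half-lives of the inhibitor after it is stopped. Then: "After the washout of the inhibitor is complete, the olaparib dose can be re-escalated".

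The trial uses tablets at 300 mg twice daily (section 5.4, Table 2), supplied as 100 mg and 150 mg tablets (section 9.1.1.2.1). Footnote 6 of the flow chart in section 6.1 directs sites: "PLEASE SEE SECTION 5 FOR DETAILS REGARDING OLAPARIB AND PEMBROLIZUMAB ADMINISTRATION". Table 5 (Olaparib Dose Modifications) sets 200 mg and 100 mg twice daily as steps for toxicity only.

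**The concern.** The two sections cover the same trigger, inhibitor classes and starting dose, yet each dose differs by 50 mg twice daily. No clause gives either section precedence, so the dose depends on which one a site reads. The section that sites would naturally open is the one that agrees less well with the interaction data printed in the protocol.

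The situation is realistic. Section 4.3.2.2 lists clarithromycin, ciprofloxacin, erythromycin and fluconazole among the inhibitors, and Table 3 calls for prophylactic antibiotics in pneumonitis. How many patients would be affected is unknown.

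At stake is olaparib exposure in those patients. Section 4.3.2.1 describes tolerability of the tablet at up to 300 mg twice daily, and section 4.4.3 describes the combination at that dose. An AUC about a third higher lies outside that stated experience.

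**Working it through.** The protocol gives no derivation for the 5.5.1 doses, so there is no calculation to reproduce. The check is whether each pair of doses restores the AUC of 300 mg twice daily alone.

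**Inputs**

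- Strong inhibitor (section 4.3.1.1, drug interactions): "the AUC and Cmax of Olaparib increased by 2.7- and 1.4-fold, respectively, when Olaparib was administered in combination with itraconazole". Section 4.3.2.2 reports the same result as "increased mean AUC by 270% (90% CI: 2.44-2.97"). The interval shows that a ratio of 2.70 is meant, not a rise to 3.7-fold.
- Moderate inhibitor (section 4.3.1.1): "a moderate CYP3A inhibitor (fluconazole) may increase the AUC and Cmax of Olaparib by 2- and 1.1-fold, respectively". This is one simulation with no interval.
- Dose proportionality in humans is an assumption. The documents do not state it, and the animal data in section 4.3.1.1 differ by species.

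**Step 1. Relative AUC = reduced dose × AUC ratio / 300**

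| Inhibitor | Section 5.5.1 | Section 4.3.2.2 |
|---|---|---|
| Strong, ratio 2.7 | 150 × 2.7 / 300 = 1.35 | 100 × 2.7 / 300 = 0.90 |
| Strong, over the 90% CI | 1.22 to 1.49 | 0.81 to 0.99 |
| Moderate, ratio 2.0 | 200 × 2.0 / 300 = 1.33 | 150 × 2.0 / 300 = 1.00 |

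The AUC-matching dose is 300 / ratio. For strong inhibitors it is 300 / 2.7 = 111 mg (101 to 123 over the CI); for moderate inhibitors it is 300 / 2.0 = 150 mg. These lie close to the 4.3.2.2 doses.

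**Step 2. Departure from proportionality**

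Let AUC vary as dose^b, with b from 0.8 to 1.2 (assumption), and let the moderate ratio run from 1.5 to 2.5 (assumption).

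- Strong, 5.5.1: 2.44 × 0.5^1.2 = 1.06 to 2.97 × 0.5^0.8 = 1.71. It stays above 1.
- Strong, 4.3.2.2: 2.44 × (1/3)^1.2 = 0.65 to 2.97 × (1/3)^0.8 = 1.23.
- Moderate at b = 1: 5.5.1 gives 1.00 to 1.67, and 4.3.2.2 gives 0.75 to 1.25.
- Moderate, ratio 1.5 with b = 1.2: 5.5.1 gives 1.5 × (2/3)^1.2 = 0.92, and 4.3.2.2 gives 1.5 × 0.5^1.2 = 0.65.

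At the stated ratios, 5.5.1 would match full-dose AUC only with b = ln 2.7 / ln 2 = 1.43 (strong) or b = ln 2 / ln 1.5 = 1.71 (moderate).

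**Step 3. Which dose is closer to full-dose AUC (strong, b = 1)**

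On the arithmetic scale, 100 mg is closer when the ratio exceeds 2 / (1/2 + 1/3) = 2.40. On the ratio scale the cut-off is √6 = 2.449, just above the lower confidence limit of 2.44. So 100 mg is closer over essentially all of the interval, but not quite all of it on the ratio scale.

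**Step 4. Cmax relative to full dose**

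- 5.5.1: 150 × 1.4 / 300 = 0.70 (strong); 200 × 1.1 / 300 = 0.73 (moderate).
- 4.3.2.2: 100 × 1.4 / 300 = 0.47 (strong); 150 × 1.1 / 300 = 0.55 (moderate).

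**Step 5. Patients already reduced under Table 5**

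Neither section addresses them. For a patient at 200 mg twice daily who starts a moderate inhibitor, the 5.5.1 figure is no reduction: AUC becomes 200 × 2.0 / 200 = 2.0 times that of the patient's own dose, and 200 × 2.0 / 300 = 1.33 times that of the 300 mg dose that was not tolerated. For a patient at 100 mg twice daily, both 5.5.1 figures exceed the current dose.

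**The case against.** The strongest reply is that 5.5.1 cites the package insert, which is not available here, so the documents cannot settle which pair is right. That stands, and it is why the insert check comes first. It does not remove the conflict: whichever pair is right, the other section needs changing.

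It can also be said that 5.5.1 governs as the conduct section and 4.3.2.2 is only background. That is probably how sites would read it, but it is a judgement. Footnote 6 speaks of administration, not interactions, and 4.3.2.2 is itself worded as a dosing instruction.

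The exposure argument has limits that stand. Proportionality is assumed, the moderate ratio is a single simulation, and within the assumed ranges the moderate result under 5.5.1 crosses 1. On Cmax, 5.5.1 is the closer of the two to full dose, and the documents do not say whether AUC or Cmax drives toxicity. Olaparib is held for grade 3 or 4 toxicity attributed to it, and laboratory tests precede each pembrolizumab treatment (flow chart, footnote 9), which limits harm.

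A reader might infer that 5.5.1 directs sites to raise the dose of a patient already at 100 mg twice daily. It does not: it speaks of reducing. Step 5 shows a gap in the rules, not a second contradiction. Likewise, 5.5.1 omits the washout and re-escalation rules but does not contradict them.

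**Conclusion.** The conflict is certain: the two sections give different doses for both inhibitor classes, with no rule of precedence. Under dose proportionality, 5.5.1 leaves AUC about 35% (strong; 22% to 49% over the CI) and 33% (moderate) above the full-dose level, whereas 4.3.2.2 brings it to 0.90 and 1.00. The strong result stays above full dose for b between 0.8 and 1.2. The moderate result is weaker and can fall below full dose if the true ratio is near 1.5.

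Two stronger readings are not supported. One is that 5.5.1 has been shown to harm patients: higher AUC is calculated under an assumption, Cmax remains below full dose, and toxicity is inferred. The other is that 4.3.2.2 has been shown to be correct: it fits the protocol's AUC data better, but the cited insert has not been seen. Response rate, sample size and error rates are not affected.

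**What to change.** Check the tablet doses against the package insert that 5.5.1 cites. Then state one set of doses in 5.5.1 and replace the dose text in 4.3.2.2 with a cross-reference. Unless the insert says otherwise, 5.5.1 should provide that:

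- If the inhibitor cannot be avoided, olaparib is given at 100 mg twice daily with a strong and 150 mg twice daily with a moderate CYP3A inhibitor.
- The reduced dose continues for 5 (strong) or 3 (moderate) half-lives of the inhibitor after it is stopped. The patient then returns to the dose that would otherwise apply, including any Table 5 reduction required for toxicity during inhibitor use.
- The same doses apply to patients already on an inhibitor at entry, whom the exclusion criteria do not rule out by name. Their dose after washout is 300 mg twice daily, subject to the same Table 5 reductions.
- Starting an inhibitor never leads to a higher olaparib dose. For patients already at 200 mg or 100 mg twice daily, the dose is agreed with the sponsor. The documents give no rule for these patients, so this is a proposal for the sponsor to settle.

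Both doses can be made from the supplied tablets. The cost is one check, wording in two sections and a site notice, with no change to design or analysis.

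The downside is lower exposure than under 5.5.1: AUC about 0.90 (strong) and 1.00 (moderate) of full dose, and Cmax about half (0.47 and 0.55). Under the assumed ranges AUC could be as low as 0.65 with a strong inhibitor. With a moderate one it could be 0.75 if exposure is proportional, or 0.65 if b is also 1.2.
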